Overview: The initial components of the study will be performed over 6 days at baseline to 1) screen subjects for inclusion in the study and 2) obtain baseline measurements, with all studies conducted at the Cardiopulmonary Lab, Eugene, OR. These screening and baseline studies will be followed by 4 weeks of placebo or drug interventions (Cardiopulmonary Lab, Eugene, OR) and 14 days living at high altitude (Breckenridge or Leadville, CO). Within 1 week after returning to Eugene, OR, post-altitude measures will be made. Refer to Figure 1 below for a schematic representation of the timing and location of measurements. Each subject, regardless of intervention arm, will perform all protocols described below. All screening in Eugene, OR is scheduled for 6 days, but screening could take up to 10 days in the case of equipment malfunction or if the subject prefers to spread tests out over additional days.

* Indicates protocol that will be done on either day listed in early or mid altitude measures

What follows is a detailed description of each study day:

BASELINE: EUGENE, OR RESEARCH SITE

All studies done in Eugene will be done in either laboratory space within Pacific Hall and/or on running tracks and trails within the Eugene/Springfield metropolitan area or very close to this community.

Any subject with childbearing potential will be required to take a pregnancy test on VO₂max days and Hemoglobin mass testing days (both at baseline and altitude) as the other testing days will not involve any activity that would otherwise affect the fetus.

Day 1 – Informed consent, medical History, blood draw: Cardiopulmonary Lab, Eugene, OR (~60 min)

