Subjects who express interest in the study will have any initial questions answered on the phone or over email, depending on subject preference. Those interested in continuing with the study will arrive to the lab, and subjects will undergo informed consent and complete a self-report health history questionnaire, and complete a menstrual cycle history questionnaire (biological women only) (~30 min). Subjects will have the option to undergo informed consent remotely prior to arriving to the lab (see 'Informed Consent Process' below) but will complete all other paperwork, including signing the informed consent, upon arrival to the lab. Menstrual cycle history will be documented for control purposes for blood biomarker analysis, although subjects will not be required to be in a certain phase for testing, nor will they be excluded for contraceptive use.

After completing paperwork, subjects will undergo physical examinations by either a Nurse Practitioner or Physician Assistant 25 mL blood draw for iron, ferritin, transferrin, basic metabolic panel, and complete blood count measurements to be analyzed by QUEST. Subjects will be asked to either give or deny permission to the [name] Lab to re-contact them after the end of the study. Lastly, subjects will be asked to use an online Qualtrics survey, which will be emailed to every consenting subject, to log daily exercise activity for the duration of the study. (~30 min).

Day 2 – Army Physical Fitness Tests (APFTs): Cardiopulmonary Lab, Eugene, OR (~60 min)

Subjects will perform a modified version of the Army Physical Fitness Tests (APFTs) outdoors at the University of Oregon. The APFT will include 2 minutes of push-ups and sit-ups and a 5k run. Total time ~1 hour.

Day 3 – Lung function, cardiac screening, blood draw, Acute Mountain Sickness (AMS) questionnaire with finger saturation, and cognitive function testing: Cardiopulmonary Lab, Eugene, OR (~125 min)

Subjects will perform pulmonary function testing (~15 minutes) and cognitive function testing (~20 minutes).

Subjects will have an intravenous catheter (IV) placed. Subjects will then undergo comprehensive ultrasound screening. Amount of blood flow travelling through the PFO/ASD and IPAVA will be graded using saline contrast echocardiography while the subject is breathing room air. Pulmonary artery pressure, cardiac output, and TAPSE will also be measured using ultrasound (~60 minutes).

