Subjects will perform hemoglobin mass (Hb mass) and p50 measures (~75 minutes). This measurement involves placing an IV and drawing an additional 10 mL of venous blood. Any subject with child bearing potential will be required to take a pregnancy test prior to Hb mass testing. In addition, subjects will have baseline venous blood drawn (60 mL of venous blood will be analyzed for various biomarkers and 5 mL for sickle cell screening to be analyzed by QUEST). Dried Blood Spot samples will be taken utilizing a commercially available dried blood spot sampling device (80 uL) (TASSO, Tasso Inc, Seattle, USA). Dried blood will be analyzed for HGB, CD71/Band3, ESAs, and reticulocytes. Total Blood drawn for this day of ~76 mL.

Drug intervention, Eugene, OR

For the 4 weeks immediately prior to the scheduled departure date, subjects will arrive at the Cardiopulmonary Lab as required by their intervention schedule (see 'Drug Intervention' below for details) to receive their assigned intervention via a sub-cutaneous injection and/or intravenous

injection. After the last dose, subjects will have venous blood drawn (~60 mL) prior to departure to Colorado for measurements of various biomarkers. A dried blood drop sample (80 uL) will also be taken.

COLORADO FIELD SITE:

All studies performed in Colorado will happen in laboratory space created by the investigators and/or on running tracks and trails in or very near Leadville or Breckenridge, CO.

Early high-altitude measures: Days 1-3

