5k run: The 5-kilometer run will be performed as part of the APFTs at baseline (see above) and on its own on days 1, 7 and 13 in Colorado. The run will be performed on a 400 m track or local running trail (Pre's trail) in Eugene, OR and on the high school track or local paved trails near the research site in Colorado. Subjects will be asked to complete the run as fast as possible while being timed.

Drug intervention: In a single-blind, randomized, placebo-controlled design, subjects will receive a placebo (saline placebo), iron, or erythropoietin.

Iron. Volunteers will receive an intravenous injection of Fe(III)-hydroxide sucrose (200 mg) or placebo twice before high altitude exposure, once 4 weeks and once within several days before traveling to high altitude. All subjects will report to the lab as if they are receiving iron, but only those randomly assigned to the iron arm will receive iron. The remaining subjects will receive intravenous saline. This is infused over the course of approximately 2-5 minutes. This is the same dose shown to prevent AMS, and to block hypoxia-induced pulmonary hypertension²⁸. All subjects, regardless of whether they receive iron or placebo, will remain in the lab for an additional 15 minutes after administration to ensure they do not have an allergic reaction (see risks below) and to ensure placebo subjects are blinded to the treatment.

EPO. Volunteers will receive a sub-cutaneous injection of epoetin alpha 150 IU/kg injections given weekly (50 IU/kg 3 x week) for three consecutive weeks prior to high altitude exposure. This dose and timing match the AMS prevention study protocol of Heo et al.¹¹

To ensure subjects are blinded to the intervention, all subjects will have the same intervention schedule. For those in the iron group, they will come to the lab 3x per week as required by the EPO intervention schedule, for example, and receive saline interventions. For those in the EPO group, they will come to the lab one time 4 weeks prior to departing to Colorado to receive a placebo injection while the iron group receives their iron injection. The placebo group will receive saline at all visits.

The table below provides the intervention schedule for each group. Blue indicates the placebo group, red indicates the iron group, and green indicates the EPO group.

	Sunday	Monday	Tuesday	Wednesday	Thursday	Friday	Saturday
4 weeks until departure				Saline Iron Saline			

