VO₂MAX testing: Subjects will perform a VO₂max test where they exercise to volitional exhaustion. Criteria for terminating a VO₂max include achieving: 1) heart rate >85% of age-predicted max (220-age), 2) a plateau in oxygen consumption and/or a respiratory exchange ratio >1.15; all of these criteria are continuously monitored on our metabolic system and Nellcor pulse oximeter. This carries the rare risk of dizziness, confusion, nausea, fatigue, difficulty breathing, abnormal heart rhythms, stroke, heart attack, and sudden death. In subjects less than 35 years old, the risk of sudden death of all causes is estimated to be 1 in 133,000 for men (Van Camp et al MSSE 1995). In this study only 100 of 136 deaths with identifiable causes were caused by cardiac events, so this estimate of risk may overestimate incidence of cardiac events. In the event of a cardiac event, research personnel will respond in a manner appropriate to their level of training. All graduate students, study coordinators, and PIs are minimum CPR/AED/first aid certified and will therefore immediately call emergency services and perform CPR if appropriate. The overall risk of sudden death caused by a heart problem for all ages and sexes is estimated to be 1 in 15,000 to 18,000. (Source: American College of Sports Medicine - ACSM). As such, the **probability** of the adverse reactions discussed above is low, and the **severity** is very low (e.g. dizziness) to very high (e.g. sudden death).

Additional exercise tests (APFTs, 5k run, and rucksack carry): Hard exercise has inherent risks associated with it, including stroke and heart attack. These risks are very low in young, healthy individuals (less than 0.00006%). Subjects may also feel dizzy, lightheaded, or unusually winded. These symptoms can be worse during exercise at high altitude. If subjects feel faint or feel like they

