can't get enough oxygen, subjects will be instructed to tell study personnel as soon as possible. For field exercise tests, like the rucksack carry, research personnel will be stationed at various points along the course, including the start point, turn-around point, and various mid-way points. All research personnel will be equipped with subject lists, and each subject will wear an identifiable running number on their clothing. Therefore, if a subject feels faint during this test, they will be close to the aid of research personnel and easily identifiable to the research team. Subjects may experience muscle injury and stiffness following exercise. Proper warm-up and cool-down procedures will minimize the chances of this occurring.

Risks associated with core temperature pill: The risks of using the temperature pills include mechanical injury to the mucus membranes if adequate care is not used. Risks of the temperature pill will be minimized by explaining the procedures to the volunteers. Additionally, ample lubricant (suppository) or water (oral) will be provided to the volunteer. Volunteers with history of obstructive diseases of the gastrointestinal tract including diverticulosis, diverticulitis, inflammatory bowel disease, peptic ulcer disease, Crohn's disease, ulcerative colitis, or previous GI surgery will not use a telemetric pill.

Hypercapnia during rebreathing tests: Risks associated with breathing hypercapnia (high carbon dioxide) at rest include feeling light-headed, headache, fatigue, dizziness, shortness of breath. Subjects will be monitored with a peripheral estimate of arterial oxygen saturation using a forehead monitor to ensure you are well oxygenated and we will continuously monitor inspired and expired oxygen and carbon dioxide levels. As such, the **probability** of the adverse reactions discussed above is moderate, and the **severity** is minimal.

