Participants will be given a "covid-19 travel bag" which will include one 4 oz bottle of hand sanitizer (minimum 60% alcohol), 3 KN95 masks, and several alcohol wipes. We will ask the participants to do the following while traveling:

- Before walking into the airport: put KN95 mask on, this will stay on the entire duration of airplane travel
- When seated on airplane use alcohol wipes to disinfect all touch surfaces by the seat including the lap tray, buckle, arm rests, overhead light/air controls, and if in window seat, the window screen pull. Then, use hand sanitizer to clean hands.
- After exiting the airport in Colorado trash the first KN95 mask and replace with a fresh one, this mask will be used for the duration of the bus ride to Leadville or Breckenridge. Use hand sanitizer.
- When seated in the bus, use alcohol wipes to disinfect all touch surfaces by the seat. Use hand sanitizer.
- Upon arrival to Leadville or Breckenridge, trash the bus KN95 and replace with a fresh mask. Use hand sanitizer.
- Participants will be given a new "covid-19 travel bag" when they depart from Colorado so that their travel back may be as safe as possible. They will be expected to follow the same protocol for traveling to Eugene as they did while traveling to Colorado.

COVID testing protocol

If at any time during a subject's stay in Colorado they experience symptoms of COVID, they will be given a COVID test and their pod will be quarantined.

Safety Equipment available in the Cardiopulmonary and Respiratory Physiology Laboratory (where all testing and screening will be performed): Phillips FRx AED, a spare AED battery, and spare AED pads, bottled oxygen and face masks, all necessary equipment to run ACLS algorithms (suction, masks, breathing bag, etc.) and ACLS drugs such as chewable aspirin, and oxygen will be administered as required by AHA and ACLS guidelines. Additionally, a standard first aid kit is also available.

Emergency Procedures: According to American Heart guidelines, in the event of an adverse cardiopulmonary event, we will begin CPR, call 911 (as directed by U of O EH&S), and will continue CPR as required until emergency medical personnel arrive. Epinephrine auto-injectors (Epi Pens) will be available if the PI and colleagues judgement and/or 911 operator supported a decision to use an Epi Pen. In addition, a separate emergency procedure document is included.

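### The only named AED is listed for the Eugene laboratory, described as the site of all testing, but six 5k/APFT efforts per completer are run elsewhere with neither an AED nor an on-site physician named

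*Combined protocol and SAP*

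**What the plan says.** The equipment list in Section G (Safety Equipment) opens: "Safety Equipment available in the Cardiopulmonary and Respiratory Physiology Laboratory (where all testing and screening will be performed". It names one AED with spare battery and pads, oxygen, airway equipment and emergency drugs.

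Other sections place testing elsewhere:

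- Section C, Baseline: Eugene studies take place in "either laboratory space within Pacific Hall and/or on running tracks and trails within the Eugene/Springfield metropolitan area".
- Section C, Day 2: "Subjects will perform a modified version of the Army Physical Fitness Tests (APFTs) outdoors at the University of Oregon".
- Section C, Colorado Field Site: studies take place in "laboratory space created by the investigators and/or on running tracks and trails in or very near Leadville or Breckenridge, CO".
- Section C, 5k run: the run uses a track or trail "in Eugene, OR and on the high school track or local paved trails near the research site in Colorado".
- Section C, Rucksack carry: the course is a mountain trail from about 10,500 to 12,500 feet.

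Field cover is described in part. Section G (Additional exercise tests) says that for field tests such as the rucksack carry "research personnel will be stationed at various points along the course". Under Altitude associated risks, the rucksack course has a physician with a vehicle, oxygen and a first aid kit, plus radios and cell coverage. Colorado generally has oxygen, transport and nearby hospitals.

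Outside the laboratory list, AED appears only as a staff qualification. Under VO₂max testing, graduate students, coordinators and "PIs are minimum CPR/AED/first aid certified and will therefore immediately call emergency services and perform CPR if appropriate". Section G (Emergency Procedures) adds that a separate emergency procedure document exists.

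**The concern.** A reader who relies on the Safety Equipment paragraph would conclude that a defibrillator is at hand for every test. On the plan's own schedule it is documented for one type of all-out effort, the VO₂max test.

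The event that matters is exertional cardiac arrest, where a defibrillator changes what bystanders can do. If staff follow the text as written, an arrest on a running track gets CPR and an emergency call or, in Colorado, vehicle transport quoted at 5 to 20 minutes. The Leadville part of that range (5 to 10 minutes) is given alongside the hospital's distance from the lodging, not from the running venue. The plan itself lists stroke and heart attack as risks of the APFT, 5k and rucksack tests. Subjects are healthy volunteers with no expected health benefit, so inexpensive protection is reasonable to expect.

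**Working it through.** The plan gives no count of efforts by venue, so there is no figure to reproduce. The count below takes each test run to exhaustion or as fast as possible from the day-by-day schedule in Section C.

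**Step 1. Efforts per completing subject**

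| Effort | Number | Dosing | Venue | Cover named for that venue |
|---|---|---|---|---|
| Day 2 modified APFT with 5k | 1 | before | outdoors, Eugene | none |
| Day 4 VO₂max | 1 | before | laboratory | AED, oxygen, life support equipment |
| Day 5 repeat 5k | 1 | before | track or trail, Eugene | none |
| Altitude days 1, 7, 13: 5k | 3 | after | track or paved trail, Colorado | general Colorado oxygen, transport, hospitals |
| Altitude days 2, 8, 14: rucksack | 3 | after | mountain trail | physician, vehicle, oxygen, first aid kit; no AED named |
| Post-altitude 5k | 1 | after | Eugene, track or trail (inferred) | none |

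Total: 1 + 1 + 1 + 3 + 3 + 1 = 10, of which 9 are outside the laboratory.

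The post-altitude venue is an inference. Section C (Post-altitude measures) has subjects return to the laboratory to repeat the 5k, while the 5k run entry puts Eugene runs on a track or trail.

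**Step 2. Separate the rucksack carries**

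Field efforts with neither an AED nor an on-site physician named: 9 − 3 = 6, made up of 3 in Eugene and 3 in Colorado. After dosing: 3 Colorado runs + 1 post-altitude run = 4 of the 6. If the inferred post-altitude venue is dropped, 5 remain, 3 of them after dosing.

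**Step 3. Expected events**

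Inputs: 80 completers (Section C, Day 5) and the risk figures in Section G. For these exercise tests the plan says: "These risks are very low in young, healthy individuals (less than 0.00006" per cent, which is 0.0000006. Under VO₂max testing it quotes 1 in 133,000 (men under 35) and 1 in 15,000 to 18,000 (all ages and sexes). The plan does not state whether the figures are per effort or per person, so both readings are shown.

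| Risk figure | Per effort: 80 × 9 = 720 | Per subject: 80 |
|---|---|---|
| below 0.0000006 | 720 × 0.0000006 = 0.00043 | 80 × 0.0000006 = 0.00005 |
| 1 in 133,000 | 720 / 133,000 = 0.0054 | 80 / 133,000 = 0.0006 |
| 1 in 18,000 | 720 / 18,000 = 0.040 | 80 / 18,000 = 0.0044 |
| 1 in 15,000 | 720 / 15,000 = 0.048 | 80 / 15,000 = 0.0053 |

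The overall range is about 0.00005 to 0.05. For the six 5k/APFT efforts alone, the per-effort reading gives 80 × 6 = 480 efforts, so 480 × 0.0000006 = 0.0003 to 480 / 15,000 = 0.032.

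**Step 4. Sensitivity to screening**

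Counting completers only omits people screened but not taken to Colorado. If all 300 possible screenees ran the APFT and 100 repeated the 5k, field efforts would be 300 + 100 + 80 × 7 = 960, and 960 / 15,000 = 0.064. The answer stays well below one event.

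**The case against.** The strongest reply is that the gap may not exist in practice. The plan refers to a separate emergency procedure document, the natural place for equipment by site, and it was not available for this review. The contents of the field first aid kit are not itemised. Nothing says the laboratory AED stays behind when staff go to a nearby track. This stands: the text shows an unnamed device, not a proven absence.

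Three stronger readings are tempting but are not supported.

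- **That 9 of 10 all-out efforts are without emergency cover.** The count by venue is right, but it pools the rucksack carries, which have a physician and vehicle on the course and a reported history of over 300 runs without a medical adverse event, with the less covered 5k/APFT runs.
- **That the field is singled out because no written emergency response includes an AED step.** The VO₂max response and the Emergency Procedures paragraph omit the step even for the laboratory, where the device is listed. The omission is worth repairing but says nothing specific about the field. The plan also invokes American Heart guidelines, which may imply AED use.
- **That the timing after dosing shows a drug-related hazard.** The count applies to every completer, including the placebo arm, and no such link is shown here.

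It is also fair to say that the upper end of the event range uses a rate for all ages and sexes, whereas these subjects are fitness-screened adults aged 18 to 40. The plan's own figure for these tests gives at most 0.0004. Nothing in the point touches outcomes, randomisation or analysis.

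**Conclusion.** The point holds in a limited form. The parenthesis in Safety Equipment is inaccurate, and the only named AED is listed on that premise. Six 5k/APFT efforts per completer, four of them after dosing, have neither an AED nor an on-site physician named; the three rucksack carries lack only a named AED. Well under one event is expected on any reading, so the case rests on the potentially fatal consequence and the low cost of the remedy, not on likelihood.

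The conclusion assumes that the post-altitude 5k is run on a track or trail and that 80 subjects complete every effort. It is confined to the text available. This is a cheap improvement for patient safety, of minor severity.

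**What to change.** 1. In Section G (Safety Equipment), restrict the parenthesis to laboratory visits.
2. State that a portable AED will be present at each 5k/APFT venue in Eugene and Colorado, and in the vehicle on the rucksack course.
3. Add the device to Emergency Procedures, for example: begin CPR, call 911, send for and attach the AED.
4. If the separate emergency procedure document already provides this, correct the parenthesis and cross-reference that document instead.

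The cost is a few lines of text and one or two extra portable AEDs, since the plan lists one. A single unit could serve both Colorado courses, because a group's 5k (days 1, 7, 13) and rucksack carry (days 2, 8, 14) fall on different days; this assumes no overlapping groups use both courses on one day. A further unit is needed for the Eugene running venue if the laboratory is in use at the same time. Graduate students, coordinators and principal investigators are already AED-certified, so no extra staff, training or subject procedure is required.
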